## SUBJECT SELECTION

### I. Target population

We propose to study bipolar depressed subjects (BPD) whose depression has failed to remit following one or more adequate trials with an antidepressant, or who are experiencing a breakthrough depressive episode in spite of being maintained on a mood stabilizer and/or an atypical antipsychotic agent. Manic/hypomanic symptoms must have responded adequately to a mood stabilizer other than lithium. Subjects will be maintained on a mood stabilizer and/or atypical antipsychotic throughout the proposed study. Subjects who are maintained on lithium will not be included since there is a potential adverse interaction with celecoxib.

The following eligibility criteria are designed to select subjects for whom protocol treatment is considered appropriate. All relevant medical and non-medical conditions should be taken into consideration when deciding whether this protocol is suitable for a particular subject. Re-screenings may be permitted at the discretion of the PI.

### II. Inclusion Criteria

- Male or female of any race and 18 - 65 years of age at time of screening visit.
- Diagnosis of BPD I or II (DSM-IV-TR (296.52, 296.53, 296.89) without significant co-morbid secondary medical or psychiatric diagnoses.

- Depressive symptoms that failed to remit in response to antidepressant therapy OR current breakthrough depressive episode in spite of being maintained on a mood stabilizer and/or an atypical antipsychotic agent.
- Managed mania/hypomania with a mood stabilizer other than lithium, or an atypical antipsychotic.
- A minimum score of 18 on the Hamilton Depression Scale (HAM-D), 17-item.
- Willingness to institute lights-out at 11:00pm hours on the nights before blood drawings.

### **III. Exclusion Criteria**

- Any abnormal findings on the physical exam, ECG, blood/urine or minor infections.
- Abnormal results on liver or bone marrow function as indicated by liver function or CBC with differential blood tests.
- Any pre-existing physical pain condition, including fibromyalgia.
- History of peptic ulcer complicated by perforation, hemorrhage, or obstruction; symptoms of peptic ulcer within 4 weeks of enrollment date.
- Substance abuse or dependence during the preceding 12 months.
- Clinically significant hypertension, anemia, liver disease, kidney disease, arthritis, diabetes, recurrent migraines, epilepsy, stroke, gum disease, autoimmune disease. Based on the judgment of the PI, a risk assessment should be done if a subject meets any of this clinical criteria but is otherwise suitable.
- Current use of lithium.
- Current use of a stimulant.
- Current use of any anticoagulant agents.
- Current use of nicotine-containing substances. Subjects who stop using nicotine-containing substances more than 1 month prior to assessment may be considered for the study.
- Certain steroids including use of hormonal birth control and any systemic or topical corticosteroids (hormone replacement therapy will be allowed).
- Unwillingness to refrain from H2 receptor antagonists, non-aspirin NSAIDs, ginko biloba, vitamin E or fish oils, or aspirin over 81 mg/day.
- Sensitivity or allergy to the study medications.
- Need to receive agents that are contraindicated in combination with celecoxib or escitalopram.
- Unwillingness to fast and abstain from caffeine on mornings of blood drawings.
- A sleep disorder other than insomnia or hypersomnia as a distinct symptom of MDD.
- Inability to commit to the follow-up visits between 8:30am and 12:00pm.

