## STUDY PROCEDURES

### Schedule of Events

Procedure	Screen 1	Screen 2	Baseline	Week 1	Week 2	Week 4	Week 8
Consent	X						
Assign Subject ID	X						
MINI	X						
HAM-D/HAM-A/MADRS	X*	X*	X	X	X	X	X
CGI/CSSRS/AdverseEvents/CSULGIE	X		X	X	X	X	X
Self-Assessment Packet			X	X	X	X	X
Dispense Study Medication		PBO	X	X	X	X	X
Physical Exam	X						X
Drug Screen and Pregnancy Test	X						X
Routine Clinical Labs	X						X
Research Blood Draw			X			X	X
CBC/PT/PTT Monitoring	X				X	X	X
Pulse Wave Analysis			X			X	X

Heart Rate Variability			X			X
Albuterol Challenge			X			X
Pulse Wave Velocity			X			X
Saliva Sampling		X	X	X	X	X

\*HAM-D only.

Routine Clinical Labs include complete blood count, complete metabolic panel, lipid profile and thyroid function.

The following assessments are included in the self-assessment packet:

- Beck Depression Inventory (BDI)
- Beck Anxiety Inventory (BAI)
- State/Trait Anxiety Inventory (STAI)
- Spielberger Anger Expression Inventory (STAXI)
- International Physical Activity Questionnaire (I-PAQ)
- Quality of Life and Enjoyment Questionnaire (QLES-Q)
- The Short-Form McGill Pain Inventory (MPI)
- Perceived Stress Scale (PSS-14)

Subjects will be treated as outpatients for a total of ten weeks. Subjects must complete at least six weeks to be regarded as completers. If a subject chooses to withdraw from the study on or after six weeks of treatment, he or she will be asked to complete end-of-study assessments at that time. Those results will be carried forward for the purpose of data analysis.

Subjects will not receive any other type of therapeutic intervention (e.g., psychotherapy) during participation in the study. Such options may be offered to them at the conclusion of the study, if appropriate.

Subjects who complete the study and respond favorably will remain under the care of the LUMC physician, if they wish.

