#### Albuterol Challenge to Assess Endothelial Function

Subjects will undergo the Albuterol Challenge at Baseline and Week 8 to assess endothelium-dependent vasodilation. Albuterol (2 x 200µg) will be given by inhalation with a spacer device. The subject will be asked to slowly inhale for 50 seconds, and then hold breath for 10 seconds. After a 30 second rest, the procedure will be repeated. Albuterol induces vasodilation by way of receptors on the endothelium through a nitric oxide pathway (Hayward et al, 2002; Wilkinson et al, 2002). Pulse Wave Analysis will be performed at 0, 5, 10 and 15 minutes after albuterol treatment. Responses to the Albuterol Challenge will be defined as the maximum possible difference between Baseline augmentation index and post-treatment augmentation index.

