### **IV. Safety Assessments and Adverse Events Monitoring**

A complete physical examination with clinical laboratory assessments will be performed at enrollment and termination. Bleeding diathesis monitoring will be completed with higher frequency, as outlined in the schedule of events. Any negative clinically significant changes from the entry examination will be recorded as adverse events.

Adverse event (AE) monitoring will formally occur after weeks 1, 2, 4, and 8 of treatment. Subjects will be asked to describe health concerns since the last visit. Suicidality will be assessed at each visit by direct questioning and the Columbia Suicide Severity Rating Scale (C-SSRS).

All adverse events will be monitored until stable regardless of when the event takes place. If the event occurs at the end of the study, it will be referred to the subject's primary care physician and/or psychiatrist for continued treatment and/or follow-up.

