### **II. Evaluations of Benefits and Risks/Discomforts**

Each subject will be given a medical and psychiatric evaluation. Subjects who receive active treatment may experience greater improvement or possible remission of their mood disorder, as well as improved biomarker

levels and arterial compliance as measured by PWA. To compensate for time spent and inconvenience experienced during the study, a predetermined compensation fee will be given.

Physical risks to subjects are minimal. Discomfort may result from the blood drawing. There may be bruising at the needle site. Certain individuals may feel light-headed during venipuncture. Venipuncture will be performed when the subjects are sitting or recumbent to avoid injury. Discomfort may be experienced due to tedious questionnaires and interviews.

Side effects listed in the Physician's Desk Reference for albuterol include hoarseness, headache, tremors, and palpitations. A hypersensitivity reaction to the drug has been reported in very rare cases. To avoid this risk, subjects will be asked if they have had previous exposure to albuterol, and if they displayed a hypersensitivity reaction. If any adverse reactions are noted after the first administration, the subject will receive no further exposure to the drug.

Discontinuation of subjects' current antidepressant medication is unlikely to lead to worsening of depression or suicidal thoughts because eligible participants are only those who are already depressed whose depression has not responded despite attempts to treat depressive symptoms with antidepressant medication. Subjects will be seen one week after beginning the wash-out phase and one week after beginning the placebo run-in, allowing study staff to frequently assess the subjects' mental status while not on any antidepressant therapy in the unlikely event that subjects begin to feel more depressed or suicidal. Subjects will also be encouraged to contact study staff throughout the duration of the study if they notice any changes in their mental or physical health. If in the opinion of the investigator the patient develops serious suicide risks, the patient will be withdrawn from the study and provided treatment as appropriate. Should this occur the subject will be responsible for the costs of treatment.

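### Pregnancy is tested only at Screen 1 and Week 8, so first active dosing at Baseline relies on a result nominally 2 weeks old, and up to 4; a same-visit Baseline test is a cheap improvement

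*Combined protocol and SAP*

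**What the plan says.** **Who can enter.** The Inclusion Criteria admit "Male or female of any race and 18 - 65 years of age at time of screening visit". The Exclusion Criteria rule out "Certain steroids including use of hormonal birth control and any systemic or topical corticosteroids", with hormone replacement therapy allowed.

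**When pregnancy is tested.** In the Schedule of Events, the row "Drug Screen and Pregnancy Test" is marked under Screen 1 and Week 8. It is blank at Screen 2, Baseline, Week 1, Week 2 and Week 4. The physical examination and routine laboratory rows show the same two marks. The section on safety assessments also puts examination and laboratory work at enrollment and termination, so the pattern is not a table-reading artefact.

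**When exposure starts.** Study Design has the antidepressant taper begin at the end of Screen 1. It lasts one week, or two for fluoxetine. A one-week placebo run-in follows, which the investigator may extend by one week. Randomization is at Baseline. Study Treatments and Compliance then starts open-label escitalopram with blinded celecoxib or placebo. The vascular section adds: "Subjects will undergo the Albuterol Challenge at Baseline and Week 8".

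**What could reveal a pregnancy between the two tests.** At adverse-event monitoring, "Subjects will be asked to describe health concerns since the last visit". Subjects are also "encouraged to contact study staff throughout the duration of the study if they notice any changes in their mental or physical health". Someone who withdraws "on or after six weeks of treatment, he or she will be asked to complete end-of-study assessments at that time", which might bring the second test forward.

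**The concern.** A screening pregnancy test protects against exposure only if its result is still current when the first dose is given. Here the first test comes before the taper and the run-in, and the second comes at the end of the treatment phase. A woman who conceives after Screen 1, or whose pregnancy is too early to detect then, can go through Baseline exactly as the protocol prescribes. She would receive escitalopram, possibly celecoxib, and the albuterol challenge without a further test. The Week 8 test would find the pregnancy only after most or all of the treatment had been given.

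Active drug goes to subjects who still meet eligibility at randomization, but no scheduled procedure re-checks this item at that visit. The only listed randomization criterion concerns HAM-D non-response. The stake is participant safety. Sample size, power and the planned analyses are unaffected.

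**Working it through.** **Inputs.**
- Phase lengths, from Study Design: washout 1 week, run-in 1 week, active treatment 8 weeks.
- Variations, from the same section: fluoxetine taper 2 weeks; run-in extension of 1 week, so 2 weeks in all.
- Test visits, from the Schedule of Events: Screen 1 and Week 8.
- First active dose: Baseline.

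**The plan's own figure.** 1 + 1 + 8 = 10 weeks, which matches the stated 10-week study. The time from Screen 1 to Baseline can therefore be read from the phase lengths.

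**Current schedule.**
Age of the result at first dose = taper weeks + run-in weeks.
Interval between the two scheduled tests = that age + 8.

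| Path | Taper | Run-in | Age at first dose | Screen 1 to Week 8 |
|---|---|---|---|---|
| Standard | 1 | 1 | 2 weeks | 10 weeks |
| Fluoxetine taper only | 2 | 1 | 3 weeks | 11 weeks |
| Extended run-in only | 1 | 2 | 3 weeks | 11 weeks |
| Both | 2 | 2 | 4 weeks | 12 weeks |

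For a subject who withdraws at week 6, the interval is 2 + 6 = 8 to 4 + 6 = 10 weeks, if the end-of-study assessments include the pregnancy test.

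**With changes.**

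| Schedule | Visits with a test | Age at first dose | Intervals between tests | Longest |
|---|---|---|---|---|
| Current | 2 of 7 | 2–4 weeks | 10–12 weeks | 10–12 weeks |
| Add Baseline | 3 of 7 | 0 weeks | 2–4, then 8 weeks | 8 weeks |
| Add Baseline and Week 4 | 4 of 7 | 0 weeks | 2–4, 4, then 4 weeks | 4 weeks |

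The Baseline test removes the whole delay at first dose. It shortens the longest interval by only 2 to 4 weeks (10 − 8 to 12 − 8) and leaves 8 weeks of treatment without a scheduled test. Halving that on-treatment gap to 4 weeks needs the Week 4 test as well.

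**The case against.** The best case against the point has four parts.

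**A known pregnancy is already handled.** The Target Population section says: "All relevant medical and non-medical conditions should be taken into consideration when deciding whether this protocol is suitable for a particular subject". The Exclusion Criteria bar abnormal blood or urine findings, and the Termination Criteria let the investigator remove a subject for any condition that makes continuing unsafe or inappropriate. A reader might infer from the criteria lists, none of which names pregnancy, that the plan has no rule for a positive test. The documents do not support that. These general clauses can be applied to a known pregnancy, and the consent pages, which are not in the public text, may hold more specific wording. This part stands. The clauses cannot act, however, on a pregnancy that has not been detected.

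**The contraception line proves little.** A reader might infer that excluding hormonal methods leaves participants unprotected. It does not: other methods exist, and the consent form may require one. This part also stands, and the point does not depend on that inference.

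**Two weeks is the normal case.** Three weeks needs one variation and four needs both, and the plan gives no frequency for either. Study Design also notes, in discussing the run-in extension, that patients are seen weekly and kept in close telephone contact. That is fair on emphasis. But contact and self-report help only once a woman suspects she is pregnant, and even the standard path has no test at the dosing visit.

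**No harm is quantified.** The documents state no fetal risk for either drug and give no count of women able to conceive. This stands, and it limits the point to a low-cost improvement.

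**Conclusion.** The concern holds as a point about test timing. First active dosing relies on a pregnancy result that is nominally 2 weeks old, 3 with one permitted variation and 4 with both. The plan schedules no later test before the first dose. Since the plan itself tests for pregnancy, it is reasonable to ask for a current result at the visit where dosing is decided.

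The figures assume that visits fall on their nominal dates, as no visit windows are given, and that every subject passes through the washout week.

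A reader might go further and conclude that the protocol exposes pregnancies to a known or sizeable hazard. The documents supply neither a risk nor a number exposed, so no size of harm is claimed. Naming pregnancy in the criteria lists, or setting out contraception rules, is a drafting clarification whose need depends on what the consent form already says.

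**What to change.** Add a pregnancy test at Baseline for women able to conceive. Its result should be available at that visit before randomization, the albuterol challenge and the first dose. State that a subject with a positive result is not randomized.

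A further test at Week 4 is optional. It is the change to make if the sponsor also wants to shorten the on-treatment gap from 8 weeks to 4.

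Check the consent form. If it does not already cover pregnancy and acceptable non-hormonal contraception, a sentence on each in the protocol would be useful.

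The cost is one simple test, or two with Week 4, per woman able to conceive, at visits she already attends, plus a short amendment. Research blood is already drawn at Baseline and Week 4. No total can be given. The number of women able to conceive is not stated, 70 randomized is a minimum, placebo responders stopped at Baseline could also be tested, and subjects lost to attrition are replaced. The plan gives no prices, so calling this cheap is a judgment. A contraception requirement, if it were new, might exclude a few candidates.

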### **IV. Randomization Criteria**

- Subjects must not have responded or remitted as measured by the HAM-D 17 after 1 week of treatment with single-blind placebo.

### **V. Criteria for Temporary Suspension of Study Participation Pending Clarification**

- HAM-D 17 score of less than 18 at Baseline visit, indicative of a placebo responder.
- Subject attempts suicide or seriously deteriorates.
- Develops signs or symptoms suggestive of an ulcer or kidney disease or other serious illness.
- Develops elevated blood pressure, creatinine, potassium, or decreased hematocrit.
- Requires corticosteroids, warfarin, ticlopidine, or any anticoagulant.
- Takes more than 4 doses per week of any of the following: Vitamin E or fish oils (at doses > 600 IU/day), non-aspirin NSAIDs or aspirin (>81 mg/day).

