## II. Blood Sampling

Blood samples will be drawn at trough levels after instructing subjects to ensure a 12-hour interval after the last dose in the evening preceding the morning blood draw. Plasma, serum and buffy coat will be immediately separated and frozen at -80°C for future analysis.

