### Monitoring of Possibility of Bleeding Diathesis

These measures will be obtained from blood drawn at Week 2, Week 4, and Week 8. Since the combination of an SSRI and a COX-2 inhibitor has the potential to induce bleeding diathesis, a complete blood count (CBC), prothrombin time (PT) and partial thromboplastin time (PTT) will be evaluated. Prothrombin Time and aPTT testing are performed on the Sysmex CA-7000 analyzer utilizing the scattered light detection method. The analyzer irradiates red light (660 nm) onto a mixture of blood plasma and reagent and detects the change in turbidity (when the fibrinogen is transformed into fibrin) as the change in scattered light. A curve is generated, plotting time against the amount of scattered light. This sample will be processed by LUMC Clinical Laboratories.

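### Elevated creatinine or potassium triggers suspension, but neither is scheduled to be measured between first dose and Week 8

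*Combined protocol and SAP*

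**What the plan says.** Under Subject Selection, section V (Criteria for Temporary Suspension), one criterion is met when a subject "Develops elevated blood pressure, creatinine, potassium, or decreased hematocrit". A separate criterion in the same list covers a subject who "Develops signs or symptoms suggestive of an ulcer or kidney disease or other serious illness".

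The laboratory content is defined under the Schedule of Events: "Routine Clinical Labs include complete blood count, complete metabolic panel, lipid profile and thyroid function". That row is marked at Screen 1 and Week 8 and at no visit between. Assessments, section IV (Safety Assessments and Adverse Events Monitoring) says the same in prose: "A complete physical examination with clinical laboratory assessments will be performed at enrollment and termination". It names bleeding monitoring as the part done more often.

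The bleeding subsection says of its blood count, PT and PTT: "These measures will be obtained from blood drawn at Week 2, Week 4, and Week 8". For blood samples, Assessments, section II says: "Plasma, serum and buffy coat will be immediately separated and frozen at -80°C for future analysis". The research assays listed there are inflammation biomarkers, kynurenines, drug levels and PGE2.

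**The concern.** The criterion concerns something that develops after entry, so it can act only if someone measures it after entry. For two of its four items, creatinine and potassium, the plan schedules no measurement during treatment until the final visit.

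Symptomatic kidney disease is already covered by its own criterion. What the laboratory trigger adds is the rise that causes no symptoms, and the schedule does not look for that. Celecoxib is fixed at 400 mg/day for 8 weeks, so a subject with a silent early rise would normally take the whole course before anyone saw the result. What is at stake is subject safety during dosing, not the efficacy comparison.

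**Working it through.** **Step 1. Which planned test carries the two analytes.** Only the complete metabolic panel could. The document does not list its components. That it includes creatinine and potassium is an assumption from standard usage. If it did not, there would be no scheduled measurement at all and the gap would be larger.

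**Step 2. When each item in the criterion is measured.** Inputs are the Schedule of Events and, for blood pressure, the SphygmoCor section, which records brachial pressure at the pulse wave sessions.

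| Item | Source of the value | Scheduled at | Weeks 1, 2, 4 covered |
|---|---|---|---|
| Creatinine, potassium | Routine Clinical Labs | Screen 1, Week 8 | 0 of 3 |
| Hematocrit | CBC/PT/PTT row | Screen 1, Weeks 2, 4, 8 | 2 of 3 |
| Blood pressure | Pulse Wave Analysis session | Baseline, Weeks 4, 8 | 1 of 3 |

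The table breaks lower down in the extracted text, but these rows are intact, and the prose in the safety section agrees with the laboratory row.

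**Step 3. Whether another draw fills the gap.** Weeks 2 and 4 clinical blood: blood count, PT and PTT only. Week 4 research blood: separated and frozen, with no chemistry among its listed assays. Neither does.

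**Step 4. Interval between the two chemistry panels.** From Study Design:

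- Shortest: 1 week taper + 1 week run-in + 8 weeks treatment = 10 weeks.
- Longest: 2 weeks fluoxetine taper + 2 weeks extended run-in + 8 weeks treatment = 12 weeks.

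The part on active treatment is 8 weeks in both cases.

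**Step 5. Effect of adding Weeks 2 and 4.** On-treatment gaps become 2, 4 − 2 = 2 and 8 − 4 = 4 weeks. The longest falls from 8 to 4 weeks. Treatment days left when a rise already present at a visit is sampled, out of 8 × 7 = 56:

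- Week 2: 56 − 14 = 42 days
- Week 4: 56 − 28 = 28 days
- Week 8: 56 − 56 = 0 days

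**Step 6. Number of added tests, two per subject.**

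- 70 randomized at LUMC: 2 × 70 = 140
- About 80 enrolled at LUMC, all tested: 2 × 80 = 160
- If Munich followed the same schedule: 2 × 90 = 180 for the powered total, or 2 × (70 + 30) = 200 for both sites' randomization targets

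Munich's safety-laboratory schedule is not described, so the last line is conditional.

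**The case against.** The schedule reading is not in dispute. The strongest reply is that a suspension criterion is a list of events to act on when they come to light, not a promise to measure each one at set times. It can still work through unscheduled tests, outside results or the laboratory work done at early termination. That is correct, and it limits the point to silent rises in subjects whom nobody has reason to test.

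Risk at entry is also low. The exclusions cover "Any abnormal findings on the physical exam, ECG, blood/urine or minor infections", lithium use, and unwillingness to refrain from other NSAIDs, and age is capped at 65. Clinically significant kidney disease, hypertension and diabetes are excluded too, though less firmly: "a risk assessment should be done if a subject meets any of this clinical criteria but is otherwise suitable". Adverse events are reviewed at Weeks 1, 2, 4 and 8. This stands as a reason for a minor rating, but entry screening cannot show what develops on drug.

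The safety discussion deals with cardiovascular risk, bleeding and drug interaction. It gives no rate for raised creatinine or potassium. That stands, and no number of affected subjects is claimed. The argument rests on the protocol's own decision to make these values a trigger.

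Some figures need care. The 42 and 28 days are calendar subtraction. They assume that the rise is present at the visit, that results return at once and that suspension is immediate, so they are upper limits. The 0 days takes dosing to end at Week 8, as Study Design describes, although the Schedule of Events also marks medication dispensing at that visit. Neither caveat changes the count of zero mid-treatment values.

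Finally, more testing against an undefined cut-off could interrupt dosing for trivial rises, and abnormal values might hint at allocation. Both are real but small. Blood counts and blood pressure already carry the same kind of hint.

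**Conclusion.** The concern holds as a minor, optional improvement. Followed as written, the schedule gives 0 of 3 creatinine or potassium values at the treatment visits before Week 8. That part of the suspension rule therefore cannot act by schedule on a symptom-free rise while suspension would still shorten exposure. At LUMC, 35 subjects are to receive celecoxib under this schedule.

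The conclusion rests on the metabolic panel being the only carrier of the two analytes and on active treatment lasting 8 weeks. It does not depend on an assumed event rate. Sample size, power and the HAM-D comparison do not change.

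**What to change.** Add creatinine and potassium to the clinical blood already taken at Weeks 2 and 4, and amend the Schedule of Events to match the suspension criterion. Test both arms alike, so that the testing itself says nothing about allocation. Thresholds and management stay with the investigators, though a written cut-off for an elevated value would limit suspensions for trivial changes.

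The cost is two chemistry requests per subject (140 to 160 at LUMC), at most one extra tube at each of two existing venepunctures, and one schedule amendment. The Week 2 and 4 clinical samples already go to the LUMC clinical laboratories, and no visit or needle stick is added. The document gives no prices, so calling this cheap is a judgement. The drawback is that some mild, transient elevations will appear, need clarification and may briefly interrupt dosing.
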